**ABBREVIATIONS AND DEFINITIONS OF TERMS**

ROR	Reach Out and Read
ACE	Adverse Childhood Experiences
SAHL	Short Assessment of Health Literacy
EPDS	Edinburgh Postnatal Depression Scale
StimQ	Measure of Cognitive Stimulation Provided in the Home
ERPQ	Early Reading Practices Questionnaire
BSID-III	Bayley Scales of Infant and Toddler Development, Third Edition
DialogPR-I	Dialogic Reading Practices- Infant, parent-report pilot measure

## **ABSTRACT**

### Context:

Reach Out and Read (ROR) has become a standard evidence-based primary care practice to support early literacy development of young at-risk children. It utilizes board books which are distributed at pediatric well visits along with literacy promotion and reading modeling by pediatricians. However, digital reading utilizing e-books and apps for reading on electronic devices has become popularized. We would like to address the important question of whether digital reading with e-books is as effective as reading with standard board books on early development. For this 18-month investigation, we propose to recruit 100 parent-infant dyads from 3 CHOP primary care pediatric practices (Indian Valley, Cobbs Creek and Roxborough). Healthy infants at least five months of age who are Medicaid eligible and whose parents have access to smart phones and other mobile digital devices at those practices would be recruited and randomized 1:1 to early literacy promotion using either 1) standard early reader board books or 2) digital electronic early reader books (e-books). Books would be distributed at 3 time points to coincide with well visits up to 13 months of age. Outcomes corresponding to reading behaviors (quantity and quality of joint reading) would be measured approximately 1 month after the 6, 9, and 12 month well visits. Child development would be measured when the child is between 12 and 18 months, 30 days of age. A subset of up to 40 parent infant dyads will be recruited to participate in a videotaped interaction while reading both an e-book and standard board book. Parent and child behaviors during the reading task will be coded and analyzed for differences across book type.

### Objectives:

- 1) To test the effects of digital versus standard literacy promotion on early development using a randomized controlled trial design.
- 2) To explore the reading practices and reading activities among children and their parents when comparing the use of e-books to traditional board books.
- 3) To identify themes regarding dialogical reading behaviors among parents participating in the Video Sub-study.

### Study Design:

A randomized controlled trial will be conducted comparing digital versus standard literacy. Participants will be stratified by clinic site and randomized to receive literacy promotion using 1) standard early reader board books or 2) digital electronic early reader e-books. Randomization sequences will be developed by the project biostatistician using computer-generated random numbers prior to enrollment and will be placed in sealed opaque envelopes. Randomization will ensure equivalence between groups on measured and unmeasured characteristics and is

considered to be the strongest protection against bias in study design. A total of 40 participants will be recruited between 9 and 12 months of age for the videotaped interaction and interview.

#### Setting/Participants:

In the randomized control trial, we will recruit and consent one hundred eligible parent-infant dyads, with the infant being between 5 and 7 months of age at enrollment. Eligible participants must have Medicaid insurance coverage, access to one of the three CHOP Care Network practices (Cobbs Creek, Roxborough and Indian Valley) for this 18-month trial. The video sub-study will recruit up to 40 eligible parent-infant dyads. Eligible participants will be recruited from both the randomized control trial as well as external to the larger trial from a participating clinic. Eligible participants must have Medicaid insurance coverage, access to a digital device, and present to one of the three CHOP Care Network practices (Cobbs Creek, Roxborough and Indian Valley).

#### Study Interventions and Measures:

In this intervention, parent-infant dyads randomized to the digital arm will receive developmentally appropriate e-books. Those randomized to the standard arm will receive developmentally appropriate board books. Participants will receive either the e-book or board book for their 6, 9 and 12 month well visits. The developmentally appropriate books selected for each of the 3 well visits are as follows: [name] *Hop on Pop* for the 6 month well visit, Sandra Boynton's *Barnyard Dance* for the 9 month well visit, and Margaret Wise' *Goodnight Moon* for the 12 month well visit.

In addition to the books, parent-infant dyads in both arms will be provided information on the importance of early parent-child reading activity by pediatric clinicians using the Reach Out and Read framework.

We will collect standard measures of demographics (child age, sex, race/ethnicity, maternal age, family structure, maternal education level, and family income category), maternal adversity (9 ACE questions), maternal health literacy (SAHL), and maternal depressive symptoms (EPDS) at baseline. About 1 month after the infant has, or is age-eligible for, their 6 and 9 month well visits we will collect measures of reading activity (StimQ and ERPQ). Roughly 1 month after the infant has, or is age eligible for, their 12 month well visit, the infant will receive a developmental assessment (BSID-III), along with additional measures of reading activity (StimQ, ERPQ). They will additionally complete the paper-based DialogPR-I at this visit. A video recorded reading task will be obtained for up to 40 participants. These participants will be asked preliminary questions about their reading practices at home at the time of the video session.

## **1 BACKGROUND INFORMATION AND RATIONALE**

### **1.1 Introduction**

Children who receive Medicaid are more likely to be at increased risk for language and cognitive delays. Such delays can lead to poor school readiness and disparities in educational outcomes when compared to children from middle and upper income strata. Reach Out and Read (ROR), a national program which promotes parent-child reading activities for children 6 months through 5 years of age at pediatric well child visits, has been shown to improve at-risk children's expressive and receptive language development. However, children who participate in ROR still demonstrate language outcomes that are below national averages. It is not clear whether digital literacy promotion, i.e. promotion of parent-child reading with the use of e-books, is as effective as standard literacy promotion and if it could improve poor urban children's language and cognitive outcomes.

The disparities that continue to exist among language development despite literacy promotion efforts suggest that other barriers and factors may exist that influences these disparities. While it has been demonstrated that reading to infants is imperative for appropriate language development, the differences between reading to children in an e-book format versus a standard board book format have not been explored. In a growing digital age access to e-books is ever present and investigating potential differences in early literacy outcomes is beneficial for families and pediatricians.

### **1.2 Name and Description of Investigational Product or Intervention**

The intervention will be an adapted version of the Reach Out and Read (ROR) Program, a national program that promotes parent-child reading activities for children 6 months through 5 years of age at pediatric well child visits. It will be adapted for use with parents of children from 5 to 18 months, 30 days. Digital literacy promotion will consist of the provision of developmentally appropriate standard and digital books selected specifically for all well visits from 5 months of age onwards. In this instance we define standard as the use of age appropriate board books in literacy promotion initiatives and digital as the use of mobile app based e-book versions of the same board books. It will also include follow-up contact with the parent to ascertain whether or not they encountered issues with the apps functioning, reminders to schedule and/or attend upcoming well visits, and for some parents, an interview and video recorded reading task with their infant.

### **1.3 Relevant Literature and Data**

Early childhood is a critical period in which young children attain developmental skills necessary for language function. Early stimulation of brain centers involved in language development

promotes critical neuronal connections leading to growth in language functioning. Unfortunately, language delays are common among children under age 3 years, particularly for children residing in impoverished communities. The cause of these language delays are multifactorial but in part result from deficits in parent-child verbal interactions. Twelve to sixteen percent of young children are estimated to have delays that affect language development. Differences between poor and advantaged children in language processing skills and vocabulary are evident by 18 months of age. These delays contribute to social and emotional problems and result in poor educational and functional outcomes. Lifetime costs for individuals with developmental disabilities including language deficits has been estimated to exceed \$60 billion in 2003 U.S. dollars.

Parent-child dialogic reading represents an important source of language stimulation and is rich in verbal interactions that can stimulate language development. Studies have found parent-child reading to be associated with improved language functioning and better school performance. Based on this observation, the ROR Program was established to promote parent-child reading activity. ROR is based in pediatric clinical settings and provides developmentally appropriate books to young children and encourages a discussion of the importance of reading by pediatric clinicians at well child visits from 6 months through 5 years. Evaluations of ROR have shown beneficial effects on reading activity and language outcomes. These effects translate into an increase of 1 day/week of parent-child reading activity, a 4-fold increased likelihood of reporting reading to their child, and a 4 to 9 point increase in expressive and receptive language scores respectively (a 3-6 month advance in language). For this reason, the American Academy of Pediatrics has recommended that pediatric clinicians promote early literacy development beginning in infancy.

Electronic or e-books for children have grown in popularity. They come in a number of formats including Nooks, Kindles, and iPads as well as a number of digital apps that are used on smart phones and tablets. They permit children to follow along with stories, activate games and sounds, and listen to music. Their popularity may be related to parental beliefs that e-books help promote child intellectual development. However, a recent study examining reading behaviors and comprehension among children using e-books found that e-books were associated with fewer dialogic language behaviors and lower reading comprehension compared to traditional books. However, the study was limited by only enrolling middle to upper income preschool-aged children, so it isn't clear that the findings are generalizable to younger children from low-income households.

#### **1.4      Compliance Statement**

This study will be conducted in full accordance all applicable Children's Hospital of Philadelphia Research Policies and Procedures and all applicable Federal and state laws and regulations including 45 CFR 46. All episodes of noncompliance will be documented.

The investigators will perform the study in accordance with this protocol, will obtain consent and assent, and will report unanticipated problems involving risks to subjects or others in accordance with The Children's Hospital of Philadelphia IRB Policies and Procedures and all federal requirements. Collection, recording, and reporting of data will be accurate and will ensure the privacy, health, and welfare of research subjects during and after the study.

## **2 STUDY OBJECTIVES**

### **2.1 Primary Objective**

The primary objective of the study is to discover the effects of language development of young, at-risk children in digital versus standard literacy promotion using a randomized controlled trial design. In this instance we define standard as the use of age appropriate board books in literacy promotion initiatives and digital as the use of mobile app based e-book versions of the same board books in a literacy promotion intervention.

Specific Aim 1: To determine the comparative effectiveness of digital literacy promotion to standard literacy promotion on early development among young Medicaid eligible children in the Philadelphia metropolitan area.

### **2.2 Secondary Objectives**

Specific Aim 2: To explore the reading behaviors and reading activities among children and their parents when comparing the use of e-books to standard board books.

Specific Aim 3: To identify themes regarding dialogical reading behaviors among parents participating in the Video Sub-study.

Specific Aim 4: To explore the impact of digital literacy on healthcare utilization

## **3 INVESTIGATIONAL PLAN**

### **3.1 General Schema of Study Design**

#### **3.1.1 Randomized Control Trial**

We propose to test the effects of digital versus standard literacy promotion using a randomized controlled trial design. One-hundred eligible parent-child dyads, with infants between 5 and 7 months of age, who present to one of the three CHOP Care Network practices (Cobbs Creek, Roxborough and Indian Valley) will be recruited and consented to participate in this 18-month long study. Participants will be stratified by clinic site and randomized to receive literacy promotion using 1) standard early reader board books or 2) digital electronic early reader e-books. Randomization sequences will be developed by the study team using computer-generated random numbers prior to study enrollment and will be placed in sealed opaque envelopes.

Randomization will ensure equivalence between groups on measured and unmeasured characteristics and is considered to be the strongest protection against bias in study design.

Participants randomized to the digital arm will receive the e-book version of [name] *Hop on Pop* for the 6 month well visit, Sandra Boynton's *Barnyard Dance* for the 9 month well visit, and Margaret Wise' *Goodnight Moon* for the 12 month well visit. Additionally they will receive information on the importance of early parent-child reading activity by pediatric clinicians using the Reach Out and Read framework. The appropriate e-books will be electronically gifted to the participants. Parents must have an appropriate mobile digital device such as a smart phone or tablet to download and open the digital e-books.

Participants randomized to the standard arm will receive the board book versions of [name] *Hop on Pop* for the 6 month well visit, Sandra Boynton's *Barnyard Dance* for the 9 month well visit, and Margaret Wise' *Goodnight Moon* for the 12 month well visit. Furthermore, participants will be provided information on the importance of parent-child reading activity by pediatric clinicians using the Reach Out and Read framework.

Participants in both study arms will be followed every 3 to 4 months until the infants are between the ages of 12 and 18 months, 30 days. Information on reading activities and developmental outcomes will be collected in concert with scheduled well child visits. Differences in reading activities and developmental outcomes will be assessed between groups using intention-to-treat analysis. Parents will complete measures of demographics, health literacy, and maternal depressive symptoms at baseline. Parents will also complete measures of reading activity with their infant about 1 month after the child has, or is age-eligible for, their 6, 9, and 12 month well visits. The infant will also receive a developmental assessment at the second study visit which will happen about 1 month after they have, or are age-eligible for, their 12 month well visit. At this time the infant should be between 12 and 18 months, 30 days old. Secondary data to address these study questions does not exist, which will necessitate the collection of new data as proposed here. We anticipate that this collection of rich new data will support a careful assessment of the effects of digital vs. standard literacy promotion. The HER will be reviewed for children in both arms to count the number of well child visits and examine their vaccination history.

We anticipate collecting this data in conjunction with well child visits. In our experience, low-income families can be difficult to reach for study visits, even with appropriate study incentives. By coordinating data collection with the 6, 9, and 12 month well child visits timeframes, we can increase the probability of families attending both the well visits (to receive the Reach Out and Read Program materials) and the study visits (to collect measures of reading activity and development). In a previous study of 2100 children enrolled in a study of developmental screening, we were able to achieve a >90% follow-up rate by coordinating data collection with well child visits. In addition, our research staff can check the clinic schedule to ensure families have made timely well child visit appointments and then make reminder calls to families prior to these visits to encourage parents to attend. Study visits will be held at a location that is preferred

and most convenient for the parent, including but not limited to: the clinic, a separate CHOP-based facility, the Temple Infant and Child Lab, or another location based on availability and parent preference.

### **3.1.2 Video Sub-study**

Up to 40 participants will be additionally recruited to participate in an interview and video recorded reading task. Participants will be recruited both from the larger RCT as well as from external sources (see Section 8.4). Dyads enrolled in the randomized control trial who agreed to participate in the sub-study at the time of their initial consent, and who are in the control (Traditional board book) arm, will be approached by telephone call, or the method of communication that they prefer, immediately following the time that they become age-eligible for their 9-month well visit. Participants meeting eligibility criteria and recruited external to the randomized control trial will be approached for participation at clinic appointments at one of the study sites. Participants will be continuously recruited until either the enrollment goal (40 dyads) is reached or until saturation of themes is achieved for this qualitative sub-study. Sessions, lasting approximately 45 minutes, will be held at a location that is preferred and most convenient for the parent, including but not limited to: the clinic, a separate CHOP-based facility, the Temple Infant and Child Lab, or another location based on availability and parent preference. For participants recruited from the larger study, no additional demographic data will be collected, as it will be accessed from the previously reported data. Participants recruited externally for the sub-study will complete the demographic and screening questionnaires that were previously collected by the larger study participants upon enrollment. These externally recruited participants will not participate in or be consented for participation in the larger randomized control trial.

On the day of the video sub-study session, all parents (regardless of whether or not they were recruited from within or external to the main RCT) will first be instructed to read a book with their child. This reading task will be video recorded by a member of the study staff. Parents will be asked to read to their child in the same manner that they had learned from their provider during their well-child check as part of Reach Out and Read. Parents will be receiving this instruction on dialogic reading, regardless of study arm, as part of the larger study. The selected book will be Sandra Boynton's *Barnyard Dance*, which is the same book that the participants recruited from the main RCT study will have received for their 9-month well visit. All participants will read the same book with electronic books provided on a tablet device. Participants will be randomized on the order they read the types of books (print book, basic e-book and enhanced e-book).

Following the video-recorded reading tasks, all parents will participate in a 20-minute, semi-structured, audio-recorded interview with a member of the study staff. An interview guide will be developed and piloted with parents of infants prior to use within the study. In the interview,

parents will be asked their behaviors (frequency, duration, style) and perceptions on reading to their infant and whether this would vary based on using print books and electronic books. All participants will be asked the same questions.

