### **3.1.3.2 Video Sub-study**

Children will be eligible to participate in this sub-study if they were born  $\geq 35$  weeks estimated gestational age, without neurodevelopmental disabilities or congenital malformations, with Medicaid insurance (proxy measure for poverty), and, for participants being recruited externally, at least 9 months and 0 days and no more than 12 months and 0 days at the time of enrollment. As in the randomized control trial, children who are born premature  $< 35$  weeks EGA, who have neurodevelopmental disabilities, or who have congenital malformations will be excluded, as they are at increased risk of language delays. In addition, we will exclude families who do not speak English for this sub-study, as resources are not available in this pilot to execute and code video data in additional languages.

Potential subjects will be identified from 1) participants in the randomized control trial that previously consented to participate in the sub-study, were randomized into the control group (traditional board book arm), and are age-eligible for their 9 month well visit, and 2) eligible patients recruited from the Cobbs Creek clinic who are 9 to 12 months old. For participants recruited external to the randomized control trial, study staff will identify eligible participants and, when on-site at the time of the appointment, approach participants in person at the clinic before or after their appointment with the clinician. At that time, a member of our study staff will explain the study procedures and consent the parent and infant for participation. The consenting process will include a discussion of study rationale, procedures, measures, benefits, risks, and alternatives to participation. Once they have consented to participate, they will complete a demographic questionnaire (Appendix 1), questionnaires about adverse childhood experiences (Appendix 2) and health literacy (Appendix 3), and the Edinburgh Postnatal Depression Scale (EPDS) (Appendix 4). They will also schedule the parent and child for a study visit at that time if the parent is able. Parents who are unable to be scheduled for participation at that time will be contacted by study staff via telephone to schedule the study visit.

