#### **5.1.10 Audio-recording and Videotaping of Interviews**

Parent-infant dyads recruited into the videotape sub-study will participate in a video recorded reading exercise and a brief, audio-recorded semi-structured interview. Parents will be videotaped while reading a print book and two versions (basic and enhanced) of an electronic book with their infant. As part of this exercise, parents will also be audio recorded while participating in a semi-structured one-on-one interview with a study team member. Videotaped book readings will be analyzed without transcription. Interview audio recordings will be transcribed by ADA Transcription (<http://www.adatranscription.com/>). Audio recordings will be de-identified and sent via their secure server, and subsequent transcripts will be saved on a secure server accessed only by members of the study team.

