### 6.3 Statistical Methods

Summary statistics will be obtained, and differences between digital and standard arms will be assessed using intention-to-treat analysis. Cross-sectional differences in StimQ scores between digital and standard groups at the 6, 9 and 12 month well visits will be assessed using t-tests. To determine how the effects of digital versus standard literacy is associated with language development, we will develop regression models using longitudinal data methods that adjust for correlation in BSID-III scores over time and for potential confounding by demographic characteristics. To explore the impact of digital literacy on healthcare utilization, the EHR will be reviewed to identify a subjects' number of well visits and their vaccination history.

To determine whether parent adversity, health literacy, and/or parent mental health modify the effects of digital versus standard literacy on language development, we will develop similar regression models using longitudinal data methods, but we will also fit interaction terms between study group and ACE score ( $\geq 4$ ), SAHL (high or low) and EPDS score ( $> 10$ ). To determine if parent-child reading activity mediates the association of intervention group assignment and language development, we will use mediation analysis with separate models regressing group assignment on language development, parent-child reading activity on group assignment, and group assignment on language development adjusted for parent-child reading activity.

Assuming a mean cognitive subscale on the BSID-III of 96, a power of 0.70, an alpha of 0.05, and a clinically significant difference of 7.5 points on the BSID-III between groups, we estimate that we will need to recruit a total sample size of 100 eligible children (50 in each group) to participate in the main RCT study (Figure 1). To attain thematic saturation in the Video Sub-study, we will recruit up to 40 participants 9-12 months of age. These 40 participants may be recruited external to the main study if we are unable to recruit up to 40 from the 100 enrolled in the main study in a timely fashion. All analyses will be conducted using Stata Statistical Software, version 13 (College Station, TX).

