**Figure 1**

Power	n
0.60	80
0.65	90
0.70	100

Assuming a mean cognitive subscale of the BSID-III, an alpha of 0.05, and an SD of 15.

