### **8.6.2 Gifts**

Participants will receive three books over the course of the study, one for each well visit (6 months, 9 months and 12 months). All parents will receive a small non-monetary gift of a Reach Out and Read tote bag filled with 3 additional books to thank them for participating at the end of the final study visit. Participants in the video sub-study will receive an additional book at the time of their participation.

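### The video sub-study takes trial families from the board-book arm only, before the 12-month outcomes, so one arm gets a session, a book and a payment that the other does not

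*Combined protocol and SAP*

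**What the plan says.** Two sections restrict the trial families who may enter the video sub-study. Section 3.1.2 says that those who opted in at consent "and who are in the control (Traditional board book) arm, will be approached by telephone call". Section 3.1.3.2 describes the trial source as consenting participants who "were randomized into the control group (traditional board book arm), and are age-eligible for their 9 month well visit". The inclusion list in 3.4.2.1 and the recruitment text in 8.4.2 give no arm restriction. Section 6.3 treats all 100 trial dyads as the pool: "These 40 participants may be recruited external to the main study if we are unable to recruit up to 40" from that number.

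On content, 5.1.10 states: "Parents will be videotaped while reading a print book and two versions (basic and enhanced) of an electronic book with their infant". Section 3.1.2 names the title, which is the trial's 9-month book, and says that a tablet is provided. It adds a 20-minute interview on how parents read and whether print or electronic format changes this. Section 8.6.1 adds a $50 card to a trial total of up to $70. Section 8.6.2 states: "Participants in the video sub-study will receive an additional book at the time of their participation". Section 3.1.5 says that no further instruction is given at the session.

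On timing, families are approached as soon as the infant reaches the age for the 9-month visit (3.1.2). The 9-month survey is due about 1 month after that visit. The BSID-III and the last StimQ and ERPQ are due about 1 month after the 12-month visit (3.1.1, 4.2, 6.1).

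**The concern.** The trial is meant to compare arms that differ in book format and in nothing else the study controls. Here the study itself gives part of one arm an extra contact, an extra book, an extra payment, a structured conversation about reading and a short exposure to the other arm's format, all before the primary endpoint. Intention-to-treat analysis keeps the groups as randomised but does not remove a co-intervention given to one of them.

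The protocol regards contamination as a threat: 3.1.4 sets up an EHR alert against it. That alert covers clinicians at well visits and does not reach the sub-study. Section 6.3 plans no adjustment or sensitivity analysis for sub-study participation. The reading outcomes are the more exposed ones, because they are parent-reported and two of them are touched directly by what the sub-study does. Reading activity is also the mediator in 6.3, so that analysis would inherit any distortion.

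**Working it through.** **1. Order of events, as scheduled**

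| Measurement | Relation to the video session |
|---|---|
| 6-month StimQ and ERPQ | Nominally before it; unaffected |
| 9-month StimQ and ERPQ | Order not fixed; the session can come first |
| 12-month StimQ and ERPQ | After it |
| BSID-III (primary) | After it |
| DialogPR-I | At the video visit or the second study visit, whichever is earlier (5.1.7); 4.2 lists it at both |

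**2. Consequences that need no assumed effect size**

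- *StimQ.* Section 5.1.4 says that the Read subscale asks how many books the home holds and how varied they are. An extra book in one arm can therefore enter that score directly. Its format is not stated; a print book would clearly count. Section 6.3 compares the arms by t-tests.
- *DialogPR-I.* Filmed controls can complete it from about 9 months. Digital-arm families complete it at the second visit, nominally 12 + 1 = 13 months. If filming falls at 9 to 12 months (the range in the Abstract and 6.3), a filmed control is 1 to 4 months younger at measurement. The gap between arm means is the filmed fraction times that difference: for 20 of 50 filmed, 0.40 × (1 to 4) = 0.4 to 1.6 months; for 40 of 50, 0.80 × (1 to 4) = 0.8 to 3.2 months.

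**3. The plan's own sample size**

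Inputs from 6.3: "a power of 0.70, an alpha of 0.05, and a clinically significant difference of 7.5 points on the BSID-III between groups". From Figure 1: "an alpha of 0.05, and an SD of 15". Sidedness is not stated; a two-sided test reproduces the plan.

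- n per arm = 2 × (1.960 + 0.524)² × 15² / 7.5² = 49.4, rounded up to 50, so 100 in total. This matches, and powers of 0.60 and 0.65 give 80 and 90, as in Figure 1. A one-sided test would need 76.
- Power at 50 per arm is 0.705 (normal) or 0.697 (t-based).
- Standard error of the arm difference = 15 × √(2/50) = 3.0 points.

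**4. BSID-III, illustration only**

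The documents give no effect for the session and no split between trial and external recruits. Let k be the number of filmed controls. The largest possible k is 40, and 40/50 = 80%.

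- *If the session raises exposed children's scores by s points* (s = 1 to 3 assumed), the control mean shifts by (k/50) × s: 0.4 to 1.2 points for k = 20, and 0.8 to 2.4 points for k = 40.
- *If it transfers a share e of the between-arm effect* (e = 0.10 to 0.25 assumed), the difference becomes 7.5 × (1 − (k/50) × e):

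| k | e | Difference (points) | Power |
|---|---|---|---|
| 20 | 0.10 | 7.2 | 0.67 |
| 20 | 0.25 | 6.75 | 0.61 |
| 40 | 0.10 | 6.9 | 0.63 |
| 40 | 0.25 | 6.0 | 0.52 |

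The two mechanisms need not act in the same direction. E-book exposure would dilute the contrast, while the extra book and attention could favour the control arm.

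**The case against.** The case for leaving this alone rests on the small dose. The session is one visit of about 45 minutes. If that includes the 20-minute interview, about 25 minutes remain for three versions of one title. The tablet is provided, and no e-book is stated to be given to keep. Every trial parent must already have a smartphone or tablet (3.4.1.1), so control families are not otherwise shielded from e-books. The digital arm, by contrast, is given three e-books over three visits.

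Entry is also limited: families must have opted in and must speak English (3.4.2.2), recruitment may stop at thematic saturation, and external recruitment is described as a parallel route in the Abstract, 3.1.2, 3.1.3.2 and 8.4.2. Even the largest illustrative shift, 2.4 points, is below one standard error of 3.0.

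All of this stands as a limit on size. A reader might infer that control families are coached, that they receive the digital intervention, that 80% of the arm is exposed, or that the primary result is biased by a known number of points. The documents support none of these. Section 3.1.5 rules out added instruction, and the request in 3.1.2 to read as the provider taught refers to guidance given in both arms. The 80% is a ceiling, and every point figure above rests on an assumption.

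The objection does not answer the unequal treatment itself, the extra book's route into StimQ or the difference in child age at DialogPR-I. An unknown direction makes a result harder to interpret; it does not show that the biases cancel.

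**Conclusion.** The point holds as a defect of design. As 3.1.2 and 3.1.3.2 are written, only board-book families from the trial receive the session, interview, book and payment, and they do so before the primary endpoint and the 12-month reading measures. If the unrestricted wording of 3.4.2.1, 6.3 and 8.4.2 governed instead, digital-arm families could also be filmed and the imbalance would shrink, so these sections must be reconciled.

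The effects on StimQ and DialogPR-I follow from the text. Their size depends on how many controls are filmed and when, and for StimQ also on the book's format. The effect on BSID-III is unknown in size and direction and may be small; with planned power of only 0.70 there is little margin to absorb it. This should be fixed, mainly because prevention is cheap and later analysis can only partly repair it.

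**What to change.** - **Prevent it.** In 3.1.2, 3.1.3.2, 6.3 and 8.4.2, recruit the video sub-study from external dyads. Alternatively, hold trial families' session, interview and extra book until after the second study visit. Section 3.4.2.1 sets no upper age limit for trial families, but the 9 to 12 month wording in the Abstract (Study Design) and 6.3 would need to be reconciled with later filming.
- **State one recruitment rule.** Make 3.4.2.1, 6.3 and 8.4.2 agree with 3.1.2 and 3.1.3.2 on which trial families, if any, are approached.
- **Align DialogPR-I.** For the trial comparison, collect it at the second study visit in both arms, and reconcile 5.1.7 with 4.2.
- **For families already filmed.** Record the session date. Pre-specify a sensitivity analysis that compares the arms separately among families who did and did not opt in to the sub-study at consent. That choice is recorded on the consent form (8.5) and assignment follows consent (3.1.3.1), so each comparison stays between randomised groups. Splitting by actual filming would set self-selected controls against everyone else. The opt-in strata will be small, and a difference between them could also reflect the kind of family that volunteers, so this supports the main analysis and does not correct it.

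The cost is protocol wording, plus either more approaches and baseline questionnaires at Cobbs Creek or older infants if filming follows the final visit. The external route is already described.
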